To evaluate nerve function, three tests will be conducted, a two-point discrimination (TPD) test, a hard stimulus test and soft stimulus test. For the TPD test, the patient will be instructed to close their eyes, and a caliper will be placed on the lateral aspect of the patient's chin. The calipers will start at 0 mm and be incrementally opened in .5mm increments, and the first distance felt by the patient as two distinct points will be recorded reported in millimeters. For the soft- and hard- stimuli tests, the lower face will be divided into eight regions, with four symmetric regions per side. Region 1 will be from the skin on the chin at the midsagittal plane laterally 1 cm. Region 2 will be the skin from the edge of Region 1 extending laterally 1 cm. Region 3 will be the skin from the edge of Region 2 extending laterally 1 cm. Region 4 will be the vermillion of the lower from the midsagittal plane to the commissure. The regions will be designated by an "L" for left or "R" for right, plus a number as per the above scheme. Each region will be checked for nerve function via two tests, a cotton-swab test and a two test. During the evaluation, the patient will be instructed to keep their eyes closed. The cotton-swab test will involve the skin in each region being lightly brushed in a 2cm vertical path twice per region, and the patient reporting if they feel the contact. Likewise, the toothpick test will involve the skin being slightly depressed by the edge of a toothpick in three spots separated by 1 cm each per region, and the patient reporting if they feel the contact. The responses will be recorded as positive or negative for soft (swab) or hard pressure (toothpick), by region.

Pain will be reported via use of a visual analogue scale (VAS). The patient will rate the intensity of the pain on each side of the mandible at each visit. The intensity of the pain will be from zero, meaning complete absence of pain, to 10, indicating the maximum amount of pain imaginable.

Swelling will be measured with a soft measuring tape from the tip of the chin to the lower lobe of the ear, bilaterally. The calculation of the swelling index will be done by subtracting the baseline length (from the six-week post-operative visit) to the measured length and dividing the difference by baseline length and multiplying by 100.

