### **Outcomes (primary and secondary)**

In this study, the predictor variable was the use of laser therapy versus placebo treatment after orthognathic surgery on the mandible. The primary outcome variable was neurosensory disturbance recovery by the TPD, hard and soft sensory tests. The secondary outcome variables are pain reduction, as measured by change in VAS, and swelling reduction, as measured by soft-ruler measurement of lower face.

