### **Data analysis**

The primary outcome, change in neurosensory deficit, is measured by the three clinical tests, TPD, soft-stimulus and hard-stimulus. For TPD, the difference between the LLLT group and placebo group at each time point will be compared using an independent t-test, with alpha set at .05. The soft- and hard-stimulus tests for each region will be analyzed at each time point with a chi-square test. VAS pain score and swelling index will be analyzed using independent t-tests for the measurements on each side at each time point, with alpha set at .05. Linear regression will be performed to analyze the relationship of the pain, swelling and nerve tests with age, skeletal class, direction and magnitude of mandibular movement, and inclusion of genioplasty.

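### Two swab strokes and three toothpick spots per region appear to be reduced to one positive or negative, with no rule for mixed responses; recording the count would keep the graded information at almost no cost

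*Combined protocol and SAP*

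**What the plan says.** The Study Design section of the combined protocol and SAP sets out the soft and hard stimulus tests. For these, "the lower face will be divided into eight regions, with four symmetric regions per side". For the soft test each region is "lightly brushed in a 2cm vertical path twice per region, and the patient reporting if they feel the contact". For the hard test the skin is "slightly depressed by the edge of a toothpick in three spots separated by 1 cm each per region", again with the patient saying whether the contact is felt. The recording instruction is: "The responses will be recorded as positive or negative for soft (swab) or hard pressure (toothpick), by region".

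The Outcomes section gives these tests primary status: "The primary outcome variable was neurosensory disturbance recovery by the TPD, hard and soft sensory tests". The Data analysis section says: "The soft- and hard-stimulus tests for each region will be analyzed at each time point with a chi-square test". No section says whether one, most or all of the contacts must be felt for a region to be positive, or what to do when the responses within a region disagree.

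**The concern.** The trial is about nerve recovery, and a region where one or two of three spots are felt is an intermediate state that such a trial should be able to see. A single positive or negative per region cannot show it.

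Without a rule, mixed regions may be coded differently by different assessors or at different visits. If the individual responses are kept, a convention could instead be chosen once the data are known. The choice matters because it moves the proportion positive, and with it the ability of the test to separate the arms.

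**Working it through.** **The plan's own figure.** Sample Size gives a difference of 0.5, SD 0.5 and 90% power. A two-sample t-test at two-sided 5% (sidedness assumed) needs n = 22.02 per arm, rounded up to 23, as stated. That calculation is for a continuous outcome. No design figure is given for the swab or toothpick tests, so 23 per arm is simply carried forward.

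**Contacts elicited and values kept.** Per patient and visit:
- swab: 8 × 2 = 16 responses, reduced to 8 binary results;
- toothpick: 8 × 3 = 24 responses, reduced to 8 binary results.

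**How the rule moves the event rate.** Let p be the probability that one contact is felt (an assumption; the documents give none). With m independent contacts, P(any) = 1 − (1 − p)^m and P(all) = p^m. For the toothpick, P(at least 2 of 3) = 3p²(1 − p) + p³. At p = 0.7:
- any: 1 − 0.3³ = 0.973
- two of three: 3 × 0.49 × 0.3 + 0.343 = 0.784
- all: 0.7³ = 0.343

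| p | Swab any | Swab both | Toothpick any | Two of three | All |
|---|---|---|---|---|---|
| 0.5 | 75% | 25% | 87.5% | 50% | 12.5% |
| 0.7 | 91% | 49% | 97.3% | 78.4% | 34.3% |
| 0.9 | 99% | 81% | 99.9% | 97.2% | 72.9% |

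**Allowing for correlation.** Neighbouring spots in one region should tend to agree. With a beta-binomial model at mean p and within-region correlation ρ, set s = (1 − ρ)/ρ, α = ps and β = (1 − p)s. At p = 0.7 and ρ = 0.8, s = 0.25, α = 0.175 and β = 0.075.
- P(none) = (0.075 × 1.075 × 2.075)/(0.25 × 1.25 × 2.25) = 0.238, so any = 76.2%.
- P(all) = (0.175 × 1.175 × 2.175)/(0.25 × 1.25 × 2.25) = 63.6%.

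At ρ = 0.5 the range is 85.0% to 53.6%. It closes completely only if responses within a region always agree.

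**Power in the plan's own unit.** One region at one visit, toothpick, 23 per arm, two-sided 5% assumed, normal approximation:

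| Assumed p, control vs laser | Any | Two of three | All |
|---|---|---|---|
| 0.7 vs 0.9, independent | 11% | 50% | 77% |
| 0.7 vs 0.9, ρ = 0.5 | 25% | 40% | 57% |
| 0.3 vs 0.5, independent | 41% | 52% | 24% |

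The approximation is crude near the ceiling. Under *any* at p = 0.7, the expected number of negative control patients is only 23 × 0.027 = 0.6. The ordering is the point: *any* is worst at high detection and *all* is worst at low detection.

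**Binary scores against the count.** This was simulated with 23 per arm, 8 regions × 3 spots, patient SD 1 and region SD 0.5 on the logit scale, a treatment log-odds of 1, and a Mann-Whitney test on patient totals. All inputs are assumptions.
- Baseline logits 0, 0.5, 1 and 1.5: power 31–67% for *any*, 72–77% for *all*, 75–82% for the count.
- Logit 0, separate run: 66%, 77% and 83%.
- Logit −1 (detection 1/(1 + e) ≈ 27%): *any* 73–77% over two runs, *all* 65%. The order of the binary rules reverses; the count is still highest.
- Region SD 2, logit 0: 53%, 59% and 66%.
- Patient SD 2, region SD 0.5: 30%, 31% and 34%.

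With 1,500 runs the Monte Carlo standard error near 75% is √(0.75 × 0.25/1500) ≈ 1.1 points, so the smallest gaps are within noise. The count nevertheless led in every scenario tried.

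**The case against.** **Collapse is inferred.** The recording sentence speaks of responses in the plural, and could mean that each is written down and filed under its region. The per-region chi-square makes one binary per region the likelier reading, but it is not stated outright. This stands. It does not remove the problem: keeping every contact would put 23 × 3 = 69 correlated toothpick observations per arm into a chi-square that assumes independence, and a rule would still be missing.

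**A fixed rule recovers most of the loss.** The count beats the better of *any* and *all* by only a few points, and the plan never adopts the lenient rule. This also stands. But which rule is better depends on the detection level, which will change over follow-up as nerves recover. The count avoids having to guess.

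**The simulation is not the planned analysis.** It tests patient totals, whereas the plan tests each region separately. So the simulated powers compare ways of scoring and should not be read as the power of the planned chi-square tests.

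**Graded recovery is measured elsewhere.** Two-point discrimination, opened in 0.5 mm steps, is also part of the primary outcome and is analysed as continuous. This softens the loss but does not replace the regional swab and toothpick information.

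**Bias.** A reader might infer that an unstated coding rule could favour the laser arm. The documents do not support that. Study Design blinds the assessor and keeps assignments blinded until all data are recorded and validated, so mixed regions would be coded without knowledge of arm.

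**Conclusion.** The point holds as a low-severity improvement to a primary-outcome measure. The absence of a rule for mixed responses is certain; the reduction to one binary per region is the natural reading. The consequences are lost graded information and an event rate that depends on an unstated convention.

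Two stronger inferences should be resisted. The first is that the 97%-to-34% contrast is the size to expect: it assumes independent spots and a detection of 0.7, and shrinks to about 76% against 64% at correlation 0.8. The second is that a lenient rule always drives regions to the ceiling: at low detection, as may occur early after surgery, *any* outperforms *all*.

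The advantage of the count, roughly 1 to 8 points of power over the better of those two rules and more over the worse, rests on assumed detection, effect and variance inputs. Its direction was consistent; its size is not established. The stated 23 per arm is unaffected, because it was derived for a continuous outcome.

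**What to change.** In Study Design, replace the positive/negative entry with the number of contacts felt in each region: 0–2 for the swab and 0–3 for the toothpick. Any binary definition can still be derived from these counts, whereas responses that were never recorded cannot be recovered.

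In Data analysis, sum over the eight regions to a patient total (0–16 swab, 0–24 toothpick). Make the main comparison for each stimulus a single rank-based or ordinal test of that total, specified before unblinding. Keep region-level results as description, with a written rule for how mixed responses are classified.

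The cost is a revised data-collection form and a few lines of analysis text; no extra stimuli, visits or patients are needed. The one thing given up is that region-level tests become descriptive.

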### **Outcomes (primary and secondary)**

In this study, the predictor variable was the use of laser therapy versus placebo treatment after orthognathic surgery on the mandible. The primary outcome variable was neurosensory disturbance recovery by the TPD, hard and soft sensory tests. The secondary outcome variables are pain reduction, as measured by change in VAS, and swelling reduction, as measured by soft-ruler measurement of lower face.

### **Sample Size**

Published data (13-15) examining the effect of LLLT on IAN functional recovery shows a range of improvement versus placebo. The percentage of recovery shows that the LLLT treatment led to 27.3% (n=30, not split mouth, standard deviation not reported) (13), 13% (n=12, split mouth,  $7.4167 \pm 1.62$  vs  $8.5000 \pm 1.56$ ) (14), and 15% (n= 15,  $5.12 \pm 0.59$  vs  $5.97 \pm 0.45$ ) (15) improvement in sensory function, with . Additionally, one non-placebo controlled study of patients with long-standing documented neurosensory alteration following dental surgery (12) showed 33% improvement over baseline (n=4).

Using these studies, a sample size graph (Figure 1) was plotted in R Stats Package with the effect size versus sample size, with the standard deviation set to 0.5 and power set to 0.9. In order to detect an effect size of 0.5 with a SD of 0.5 at 90% power a sample size of just over 22 is needed. Therefore, 23 subjects per arm is required.

[figure not shown]

Figure 1- Effect size vs. Sample size.

The oral surgery clinic at Jacobi Medical Center treats approximately 50 patients with orthognathic surgery of the mandible annually, and has done so routinely for the last decade. Recruiting 46 patients to participate, even accounting for potential drop outs or failure to follow-up, should prove feasible.

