The proposed LLLT protocol will use the Biolase Epic X, an InGaAsP diode laser (940nm) using the pain relief handpiece, a device which has received FDA approval (GUDID 00647529002537) for the treatment of pain, muscle relaxation and healing via increased local circulation. The LLLT will be administered to the experimental group at 30 j/cm^2. The laser will be applied extraorally, on the skin overlying the mandible. Application will be for 40 seconds per side, with 10 seconds administered in four places along the jawline, 1 cm apart starting from the gonial angle. The timing would coincide with standard post-operative care, with the first LLLT administration performed on post-operative day 1, prior to the patient's discharge from the hospital. The follow-up LLLT doses would be given at the standard post-op follow-up visits, at one-week intervals, which would be at week 1, week 2, week 3, week 4, week 5, and week 6. Patients will be seen for evaluation at week 8 and again at approximately 20 weeks post-surgery. The control group will follow the same post-op visit schedule, but receive a dummy treatment in which the laser handpiece is moved over the patient's jaw in a similar fashion as the experimental but without laser irradiation.

Nerve function, pain and swelling will be measured according to objective measures. A baseline measurement will be recorded pre-operatively for nerve function and pain. Baseline for swelling will be used from the final measurement at week 8, due to the changes in mandible length caused by the orthognathic surgery. Measurements for each outcome will also be performed on the days for which

LLLT is administered. The individual who performs the assessment will be blinded to the group to which each patient belongs.

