### Participant Recruitment

The patient pool for this study will be drawn from regular patients scheduled to undergo orthognathic surgery at Jacobi Medical Center. Patients who have been cleared for orthognathic surgery already must be in good health and understand the risks of the surgery. The only additional requirements for inclusion are 1) the planned surgery includes bilateral sagittal split osteotomies; 2) patients must be free from pre-operative inferior alveolar neurosensory deficiencies; 3) the patient cannot have an intra-operative

accidental fracture or rupture of the inferior alveolar nerve. The details of the whole orthognathic surgery will be recorded (including maxillary procedure, genioplasty, and direction of positional change of the mandible) but will not alter eligibility for enrolment in the study.

Since 2013, over 30% of the patients treated for orthognathic surgery at Jacobi Medical Center are between the ages of 15 and 18, which is in line with orthognathic surgery in general. As such, the study aims to include these patients in the potential pool of subjects. Because of the significant portion of patients under the age of 18 in general, and their inclusion will allow for age to be examined as a related factor in how healing proceeds. Their inclusion will also allow for an adequate sample size.

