### **Safety monitoring**

While low-level laser therapy has no known adverse effects, safety monitoring of the study participants will be conducted in conjunction with their normal post-operative care during the duration of their participation, which occurs at each post-surgical visit. As orthognathic post-op care is generally overseen by the Jacobi Director of Oral & Maxillofacial Surgery (OMFS), the director will serve as the safety monitor. Adverse events during post-op care are reported to the Director of OMFS and documented into the patient chart. Any patient reporting an adverse event that is deemed, by the Director of OMFS, as clinically significant, will be withdrawn from the study and provided with all appropriate treatment. If more than one patient is withdrawn from the study through this mechanism, the study will be halted.

The Director of OMFS will report to the PI any adverse events requiring removal of a patient from the study, and the PI will document the adverse effects and provide a report to the IRB.

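### The 90% power covers one comparison of means, by inference two-point discrimination at an unnamed visit; it does not extend to the soft- and hard-stimulus tests, and the target of 46 comes with no stated loss rate

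*Combined protocol and SAP*

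**What the plan says.** The combined protocol and SAP contains one sample size calculation. Under Sample Size, to "detect an effect size of 0.5 with a SD of 0.5 at 90% power a sample size of just over 22 is needed", which is rounded up to 23 per arm. The outcome measure, its units, the visit and the sidedness of the test are not stated there. On loss, the same section says only: "Recruiting 46 patients to participate, even accounting for potential drop outs or failure to follow-up, should prove feasible".

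Under Outcomes: "The primary outcome variable was neurosensory disturbance recovery by the TPD, hard and soft sensory tests". The Study Design section records the soft and hard responses as positive or negative in each of eight regions of the lower face.

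Under Data analysis, for TPD "the difference between the LLLT group and placebo group at each time point will be compared using an independent t-test", with alpha 0.05. For the other two measures: "The soft- and hard-stimulus tests for each region will be analyzed at each time point with a chi-square test". No response rate is assumed for them anywhere.

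Three further statements bear on how many patients will be evaluable. Under Study Design, "A baseline measurement will be recorded pre-operatively for nerve function and pain". Under Participant Recruitment, eligibility requires that there was no intra-operative "accidental fracture or rupture of the inferior alveolar nerve". Under Safety monitoring, a patient with a clinically significant adverse event "will be withdrawn from the study and provided with all appropriate treatment", and the study halts if this happens to more than one patient.

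**The concern.** A reader will take 90% as the power for the primary outcome as the protocol defines it. That outcome has three components, and a calculation from a mean difference and an SD can describe only the continuous one. A null swab or toothpick result, on a measure called primary in a trial described as having 90% power, could then be misread as evidence that the laser has no effect on it.

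Even for TPD, the 90% attaches to one comparison and the plan does not say which. If the visit is chosen after unblinding, the choice can follow the results. The figure also assumes nearly complete data, because the number to recruit equals the number required.

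**Working it through.** **Inputs.** Difference 0.5, SD 0.5, power 0.90 and 23 per arm (Sample Size); alpha 0.05 (Data analysis); 1:1 allocation, implied by 23 per arm and 46 in total.

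**Reproducing the plan's figure.** Standardised difference d = 0.5/0.5 = 1.0. For a two-sample t-test with n per arm, power is the probability that a noncentral t variable with 2n − 2 degrees of freedom and noncentrality d × √(n/2) exceeds the critical value. Solving for 90%:

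- Two-sided 0.05: n = 22.02, which matches just over 22 and rounds up to 23.
- One-sided 0.05: n = 17.85, which does not match. Two-sided testing is inferred from this.
- Reading 0.5 as an already standardised effect: n = 85.03, which does not match either.

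The smallest d with 90% power at 23 per arm is 0.98, so the claim holds at about 1.0 or larger.

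**What the figure can cover.** TPD is the only primary measure analysed by t-test, so the calculation is TPD by inference. Measurements fall on the laser days (post-operative day 1 and weeks 1 to 6, which is 7), and evaluations follow at weeks 8 and 20: 7 + 2 = up to 9 TPD comparisons. The soft and hard tests give 8 regions × 2 stimuli = 16 chi-square tests per visit. No input to the calculation relates to them.

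**Loss.** 2 × 23 = 46, so the only slack is the rounding of 22.02 to 23. The documents give no loss rate; 10% and 20% are assumptions. 23 × 0.9 = 20.7, so 20 or 21 evaluable per arm; 23 × 0.8 = 18.4, so 18.

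| Evaluable per arm | Power at d = 1.0 |
|---|---|
| 23 | 91.2% |
| 22 | 89.97% |
| 21 | 88.5% |
| 20 | 86.9% |
| 18 | 83.0% |

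For scale, keeping 23 evaluable per arm would need 23/0.9 = 25.6, so 26 per arm (52 in all), at 10% loss, or 23/0.8 = 28.75, so 29 per arm (58), at 20%.

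**Stimulus tests, illustration only.** One region, 23 per arm, two-sided 0.05, power from full enumeration of two binomials. The deficit rates are assumed, and the plan does not say whether a continuity correction is used.

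| Deficit, control to laser | Uncorrected | Corrected |
|---|---|---|
| 20% to 0 | 70% | 31% |
| 30% to 0.9% | 90% | 66% |

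Even near-complete removal of the deficit in a region may be missed, and the result depends on the test version.

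**Cited studies with SDs, at 23 per arm.**

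- Split-mouth study, n = 12: pooled SD √((1.62² + 1.56²)/2) = 1.590; d = (8.5000 − 7.4167)/1.590 = 0.68; power 62%.
- Study with n = 15: pooled SD √((0.59² + 0.45²)/2) = 0.525; d = (5.97 − 5.12)/0.525 = 1.62; power above 99%.

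The protocol gives units for neither. For the second it gives neither the design nor whether 15 is per arm or in total.

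**The case against.** The strongest reply is that the calculation is correct, that the protocol never claims 90% for the stimulus tests, and that the loss effect is small. All three stand. The gap is that the sample size is offered for a trial whose primary outcome includes those tests, with nothing to say that they fall outside it.

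A second reply is that the feasibility sentence may mean that 46 completers can be obtained. That reading is possible. With no rate and no larger recruitment number, the text does not settle it.

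A reader might infer that the intra-operative nerve criterion must cost some of the 46, because baseline is measured before surgery. The documents do not support that. They do not say when patients are randomised; baseline timing does not fix it, and the first laser session is on post-operative day 1. If allocation follows surgery, these patients are screening failures and cost nothing. Safety withdrawal can remove at most one patient before the study halts.

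A reader might also infer that 52 or 58 patients could not be recruited from about 50 operations a year. No recruitment period is stated, and that count is of mandibular orthognathic surgery rather than of eligible patients, so it sets no ceiling.

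Finally, naming a TPD visit for the power statement does not by itself settle which of three components is the primary endpoint. That is true, and it is a separate matter.

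**Conclusion.** The point holds as a limit on what the 90% covers, and should be fixed. The figure is right for one two-sided comparison of means at d of about 0.98 or larger with 22 to 23 evaluable per arm. It gives no assurance for the soft- and hard-stimulus tests, and the TPD visit it refers to is unstated. This part carries most of the weight.

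The loss part is minor: at d = 1.0, power is 86.9% to 88.5% with an assumed 10% loss and 83.0% with 20%.

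The documents do not support the stronger reading that the trial is too small or its planning inputs wrong. The two cited studies that report SDs point in opposite directions (62% and above 99%), and both carry the units and design uncertainties noted above. The conclusion rests on two inferences, that the calculation is for TPD and that it is two-sided. The loss rates and deficit rates are assumptions.

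**What to change.** Keep 46 patients and change the wording before unblinding:

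1. In Sample Size, Outcomes and Data analysis, name the same single TPD visit as the comparison to which the power applies, and state that the test is two-sided.
2. In Sample Size, either give the loss expected by that visit and the power at the number left (for example 86.9% to 88.5% at 10% loss, 83.0% at 20%), or state that 46 means evaluable patients, with intra-operative exclusions replaced. Say when randomisation takes place.
3. In Outcomes and Data analysis, state that the per-region soft- and hard-stimulus tests are not powered, so a null result there is not evidence of no effect. If power for them is illustrated, show it with and without continuity correction.
4. If power is shown across the cited studies, put the units and design caveat on both figures.

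The cost is a slightly less favourable stated power and one decision on the visit. Weeks 8 and 20 lie outside normal post-operative care and may lose more patients than weeks 1 to 6, which is worth weighing in that choice. No extra patients, visits or analyses are needed.
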